Rationale: The above changes were prompted by the number of suboptimally managed cases of diarrhea, one of which resulted in colitis. These changes, including the addition of adverse event assessments at Weeks 7 and 11, have been made to increase monitoring of diarrhea.

Other changes are as follows:

- Added collection of additional blood sample at 4-week Post-Surgical Follow-Up visit for ctDNA and plasma protein biomarkers analysis.

Rationale: This is aimed to enable correlation of response with biomarkers and potential identification of high-risk population(s)

- Requirement added for Target Lesion #2, if selected, to be ≥ 10 mm.

Rationale: No minimum size was previously defined; therefore, this change was made to improve clarity.

- Added additional restriction to the following exclusion criterion: “History of prior or currently active small or large intestine inflammation (such as Crohn’s disease or ulcerative colitis). *Any patient with a baseline medical condition involving the gastrointestinal (GI) tract or who may have a predisposition for GI toxicity requires prior approval from the Medical Monitor.*”

Rationale: This was added with the intention that it may further prevent patients with potential predispositions to GI side effects from being enrolled.

- Included “Investigational Agents” amongst prohibited Concomitant Therapies.

Rationale: This was not previously specified; therefore, this change was made to improve clarity.

- Added specification that there is a 4-week “wash-out” period for any other Investigational Agents prior to initiation of treatment with GDC-0032.

Rationale: This was not previously specified; therefore, this change was made to improve clarity

Additional minor changes have been made to improve clarity and consistency. Substantive new information appears in italics. This amendment represents cumulative changes to the original protocol.

PROTOCOL AMENDMENT, VERSION 4: SUMMARY OF CHANGES

GLOBAL CHANGES

Non-serious has been deleted from “non-serious adverse event of special interest” throughout the protocol.

IND number has changed from 110184 to 121658

Medical Monitor has changed from [REDACTED] to [REDACTED], M.D. Ph.D.

PROTOCOL SYNOPSIS

The protocol synopsis has been updated to reflect the changes to the protocol, where applicable.

LIST OF AUTHORS

[REDACTED], and [REDACTED] were added and [REDACTED] was removed from the list.

SECTION 1.3: BACKGROUND ON THE PI3K/AKT/MTOR PATHWAY AND BREAST CANCER

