TABLE 5: GDC-0032 Dose Modification and Management Guidelines for Diarrhea and Colitis

Table 5 has been updated to include placebo throughout: GDC-0032/*placebo*. The following was also added to the table: *For any grade of diarrhea (≥ 1), contact patient at least weekly to monitor until resolution of symptoms. If symptoms persist beyond 2 weeks despite antidiarrheal treatment (e.g., loperamide), escalate to Grade 2 management.*

TABLE 6: GDC-0032 Dose Delay and Modification Guidelines for Stomatitis and Oral Mucositis

Table 6 has been updated to include placebo throughout: GDC-0032/*placebo*.

TABLE 7: GDC-0032 Dose Delay and Modification Guidelines for Other Clinically Significant Adverse Events

Table 7 has been updated to include placebo throughout: GDC-0032/*placebo*.

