Table 5 GDC-0032 Dose Modification and Management Guidelines for Diarrhea and Colitis

Grade of Diarrhea	Dose Modification and Management Guidelines
Grade 1	
 • Manage per institutional standard of care that includes antidiarrheals.^a • For persistent Grade 1 diarrhea occurring after Cycle 2, recommend evaluation for infectious causes via stool culture.^b For noninfectious diarrhea, consider colonoscopy to evaluate for colitis. • For any grade of diarrhea (≥ 1), contact patient at least weekly to monitor until resolution of symptoms. If symptoms persist beyond 2 weeks despite antidiarrheal treatment (e.g., loperamide), escalate to Grade 2 management.
Grade 2	
 • Hold GDC-0032/placebo and initially manage with antidiarrheals.^a • Obtain stool culture for infectious workup.^b Infections (e.g., Clostridium difficile, enteric bacteria, CMV) should be treated with the appropriate antibiotic. • For persistent Grade 2 non-infectious diarrhea lasting longer than 48 hours despite treatment with antidiarrheals, treat with oral corticosteroids (20–40 mg prednisone QD starting dose with taper) or budesonide 9 mg PO QD. • If Grade 2 diarrhea occurred after Cycle 2, was a recurrent episode, or improved with corticosteroid treatment, resume GDC-0032/placebo treatment at one dose level lower upon improvement to Grade ≤ 1 and after completion of corticosteroid treatment.

Grade of Diarrhea	Dose Modification and Management Guidelines
	
 • If Grade 2 diarrhea occurred before Cycle 2, did not require corticosteroid treatment, and was an initial episode, resume GDC-0032/placebo treatment at the same dose upon improvement to Grade ≤ 1. • For Grade 2 colitis, resume GDC-0032/placebo treatment at one dose level lower upon improvement to Grade ≤ 1 and after completion of corticosteroid treatment. • If Grade 2 diarrhea does not improve after 48 hours of corticosteroid treatment, a colonoscopy is recommended to evaluate for other causes of diarrhea (e.g., CMV colitis).

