5.2.3 Adverse Events of Special Interest (Immediately Reportable to ABCSG)

Adverse events of special interest are required to be reported by the investigator to ABCSG safety department immediately (i.e., no more than 24 hours after learning of the event; see Section 5.4.2 for reporting instructions). Adverse events of special interest for this study include the following:

- Grade 4 hyperglycemia
- Grade ≥ 3 symptomatic hyperglycemia
- Grade ≥ 2 colitis or enterocolitis
- Grade ≥ 2 diarrhea
- *Grade ≥ 1 diarrhea for >2 weeks after following medical management guidelines in Section 5.1.1.4*
- Grade ≥ 3 rash
- Grade ≥ 2 pneumonitis
- Cases of potential drug-induced liver injury that include an elevated ALT or AST in combination with either an elevated bilirubin or clinical jaundice, as defined by Hy's law (see Section 5.3.5.5)
- Suspected transmission of an infectious agent by the study drug

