5.5 FOLLOW-UP OF PATIENTS AFTER ADVERSE EVENTS

5.5.1 Investigator Follow-Up

The investigator should follow each adverse event until the event has resolved to baseline grade or better, the event is assessed as stable by the investigator, the patient is lost to follow up, or the patient withdraws consent. Every effort should be made to follow all serious adverse events considered to be related to study drug or trial-related procedures until a final outcome can be reported. *With regard to the adverse event of special interest of diarrhea, it is recommended that investigators follow every adverse event of \geq Grade 1 diarrhea with weekly patient contacts (e.g., telephone calls) and follow up until resolution. Cases that do not resolve within 1–2 weeks should be aggressively managed per protocol recommendations for gastrointestinal toxicities.*

During the study period, resolution of adverse events (with dates) should be documented on the Adverse Event eCRF and in the patient's medical record to facilitate source data verification (SDV). For follow-up reports of serious adverse events and adverse events of special interest, investigators should record all follow up information immediately (i.e., within 24 hours) on the paper Serious Adverse Event reporting form and transmit to ABCSG safety department via fax. In addition the serious adverse event and adverse event of special interest follow-up information will be captured in the EDC system. If, after follow-up, return to baseline status or stabilization cannot be established, an explanation should be recorded on the Adverse Event eCRF and paper Serious Adverse Event form, if applicable.

All pregnancies reported during the study should be followed until pregnancy outcome, and they should be reported according to the instructions provided in Section 5.4.

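### Table 5 holds study drug for persistent Grade 1 diarrhea, but the grade needed to restart is already met when the hold begins, and the later Grade 2 steps may not apply

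*Protocol*

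**What the plan says.** The escalation sentence is in the Grade 1 row of Table 5: "If symptoms persist beyond 2 weeks despite antidiarrheal treatment (e.g., loperamide), escalate to Grade 2 management". The Version 4 summary of changes introduces it with "The following was also added to the table", and the amendment's rationale reads "The above changes were prompted by the number of suboptimally managed cases of diarrhea, one of which resulted in colitis".

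The Grade 2 row begins with a hold of GDC-0032/placebo, "and initially manage with antidiarrheals", and directs a stool culture. Its corticosteroid step opens "For persistent Grade 2 non-infectious diarrhea lasting longer than 48 hours despite treatment with antidiarrheals". A colonoscopy is recommended if Grade 2 diarrhea does not improve after 48 hours of corticosteroids. Three bullets then govern resumption. The one for an initial episode before Cycle 2 that needed no corticosteroids says to "resume GDC-0032/ placebo treatment at the same dose upon improvement to Grade ≤ 1". The other two, for other Grade 2 diarrhea and for Grade 2 colitis, use the same grade condition, add that corticosteroids must be finished, and restart one level down.

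Three other places bear on this:
- Section 5.1.1 describes holding for certain Grade 2 toxicities until they return to Grade 1 or less.
- Section 5.5.1 says "Cases that do not resolve within 1–2 weeks should be aggressively managed per protocol recommendations for gastrointestinal toxicities".
- Section 5.2.3 lists as immediately reportable "Grade ≥ 1 diarrhea for >2 weeks after following medical management guidelines in Section 5.1.1.4".

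**The concern.** A hold needs a condition for ending it that is not true when it starts. For diarrhea that is actually Grade 2, falling to Grade 1 or less is such a condition. For diarrhea escalated because it stayed at Grade 1, it is not. The amendment created this second kind of hold and left the resumption bullets worded for the first.

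Two things are at stake. The first is patient protection: the sentence was added because diarrhea had been managed poorly, and sites that read it differently would protect patients unevenly. The second is the data: Section 3.4.2 makes adverse events leading to dose modification, delay or discontinuation a safety outcome. With about 110 sites, counts of interruptions and reductions for persistent low-grade diarrhea would partly reflect how each site read the table.

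**Working it through.** No arithmetic applies, and the plan states no figure to reproduce. The check follows Table 5 for a patient who has had Grade 1 diarrhea for 15 days on loperamide.

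**Entry.** Fifteen days exceeds 2 weeks, so she is escalated. Study drug is held and a stool culture is taken. Her grade at this moment is 1.

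**Release.** Setting the three resumption bullets against that state:

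| Bullet (Table 5, Grade 2 row) | Grade condition | Already met at entry? | Further condition | Restart level |
|---|---|---|---|---|
| After Cycle 2, recurrent, or improved with corticosteroids | Grade ≤ 1 | Yes | Corticosteroids finished | One level lower |
| Before Cycle 2, initial episode, no corticosteroids | Grade ≤ 1 | Yes | None | Same dose |
| Grade 2 colitis | Grade ≤ 1 | Yes | Corticosteroids finished | One level lower |

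The grade condition therefore cannot set the length of the hold on any route. On the first and third, corticosteroids, if given, do set it. On the first route without corticosteroids, nothing sets the length, although the lower dose level still applies. On the second, the grade condition stands alone, so the hold can end as soon as it begins.

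**Which bullets apply to her.** Three readings are open:

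1. *Manage the event as if it were Grade 2.* Every bullet applies. After more than 2 weeks of antidiarrheals she is past the 48-hour mark, so if the diarrhea is non-infectious the corticosteroid step is triggered. If she improves on corticosteroids, the hold lasts until they are finished and she restarts one level lower. If the culture shows an infection, the step is not triggered, and an initial episode before Cycle 2 returns to the second row of the table.
2. *Bullets that name Grade 2 apply only to actual Grade 2.* The corticosteroid and colonoscopy steps fall away, but so do the resumption bullets. The hold then has no stated end in Table 5.
3. *The hold and resumption bullets apply, but the corticosteroid bullet does not.* Before Cycle 2, in an initial episode, she restarts at once at the same dose.

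**Other sections.** None settles the question. Section 5.1.1 uses the same Grade ≤ 1 endpoint. The text of Section 5.1.1.4.1 directs a hold for Grade 2 or higher and does not mention one begun at Grade 1. Section 5.5.1 calls for aggressive management under these same recommendations, with a trigger of 1–2 weeks, where Table 5 waits until 2 weeks have passed.

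**The case against.** The strongest reply is that escalation has real content. It brings a hold, a directed stool culture (at Grade 1 otherwise only recommended, and only after Cycle 2), treatment of any infection, possible corticosteroids and, on two of the three bullets, a lower dose level. This stands. A reader might infer that Grade ≤ 1 is the only release criterion and that the added sentence has no effect. The documents do not support that, because two bullets also require corticosteroids to be finished and the culture is directed whichever route follows.

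Second, it is inconsistent to apply the resumption bullets to a Grade 1 patient while denying her the corticosteroid bullet, since both are worded for Grade 2. This also stands against treating reading 3 as the plain meaning. Reading 1 has further support in the text of Section 5.1.1.4.1, which favors prompt corticosteroids for diarrhea that persists despite antidiarrheals and sets no grade limit. But the consistent alternatives are readings 1 and 2. Reading 2 leaves the hold with no end, and reading 1 still leaves the infectious, early, first-episode case with a condition already met.

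Third, improvement may be taken to require a change, so a patient with unchanged symptoms has not improved. That is a fair reading, but the target is Grade ≤ 1, which includes Grade 1, and nothing says whether a lesser change within Grade 1 or full resolution is meant. It makes the text ambiguous without settling it.

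Fourth, weekly contact continues until symptoms resolve, and the persistent event is reportable within 24 hours. Both are real safeguards, but neither says when study drug may restart.

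**Conclusion.** The point holds as an internal inconsistency in a stated rule. In all three resumption bullets the grade condition is already met when a hold begins at Grade 1. In one of the three it is the sole condition, and a literal reading then permits restart at the same dose with unchanged symptoms. On the other routes corticosteroid completion, where corticosteroids are given, and a lower dose level still operate, so the rule is weakened for part of the group it was written for and is not void.

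No number of patients can be given. Section 1.7.1 reports related diarrhea in 67% of 27 patients on GDC-0032 with letrozole, but at 6 or 9 mg capsules daily, without separating Grade 1 from Grade 2 and without durations. The conclusion does not depend on a count. It rests on Table 5 as worded and on finding no text in the protocol that adapts the Grade 2 bullets to an escalated Grade 1 episode.

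This should be corrected because it concerns patient safety and is cheap to put right. It is a needed clarification and does not threaten the trial's primary analyses.

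**What to change.** Reconcile the Grade 1 and Grade 2 rows of Table 5 with each other and with Sections 5.1.1, 5.1.1.4.1 (text) and 5.5.1:

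- For a hold begun because Grade 1 diarrhea persisted, state a release condition that is not already met when the hold starts.
- State which Grade 2 steps apply to such an episode: the corticosteroid trigger, the colonoscopy trigger and the resumption level.
- Align the 1–2 week trigger in Section 5.5.1 with the 2-week trigger in Table 5, or say how the two relate.

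The clinical criterion in each case is for the sponsor to set, and none is proposed here. The cost is a few lines in Table 5 and Section 5.5.1. Depending on what the sponsor chooses, some patients may have somewhat longer interruptions than under the most permissive reading of the present text.

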5.1.1.4.2 Management of Stomatitis and Oral Mucositis

Aggressive mouth care for oral mucositis and stomatitis with mouthwash formulations (e.g., combinations of local anesthetic, antihistamine, corticosteroid, antacid, antifungal and/or antibiotics) may also be helpful in managing symptoms, and it is recommended that these are implemented with early signs of dry mouth, Grade 1 mucositis, or Grade 1 stomatitis (see [Table 6](#)). Avoidance of spicy foods may also be helpful.

Table 6 GDC-0032 Dose Delay and Modification Guidelines for Stomatitis and Oral Mucositis

Grade of Stomatitis/Mucositis	GDC-0032/ placebo
All grades	
 Aggressive mouth care that includes mouthwash formulations (e.g., combinations of local anesthetic, antihistamine, corticosteroid, antacid, antifungal and/or antibiotics) Diet management (e.g., avoidance of spicy foods)
Grade 1	
 Monitor symptoms and initiate management (see above). Re-evaluate within 48–72 hours.
Grade 2	
 Hold GDC-0032/placebo and manage until Grade \leq 1. Restart GDC-0032/placebo at the same dose. If Grade 2 stomatitis/oral mucositis recurs, hold GDC-0032/placebo until Grade \leq 1. Restart GDC-0032/placebo at the next lower dose.
Grade 3	
 Hold GDC-0032/placebo and manage until Grade \leq 1. Restart GDC-0032/placebo at the next lower dose. For Grade 3 event that was not adequately managed upon initial presentation, consider restarting at same dose upon discussion with Medical Monitor.
Grade 4	
 Permanently discontinue GDC-0032/placebo.

5.1.2 Management of Abnormal Liver Function Tests

Some patients have experienced elevations of liver function tests (e.g., AST or ALT). Patients will be monitored throughout the study treatment for changes in liver function tests. Given the potential for hepatic toxicity, all patients must have adequate liver function as manifested by measurements of serum bilirubin, hepatic transaminases, and alkaline phosphatase for initial and continued dosing. Separate criteria for eligibility, continued dosing, and DLT are given for patients with hepatic metastases and Grade 2 hepatic transaminase and/or alkaline phosphatase levels at baseline to allow safety testing to be adequately assessed in this patient group.

For new abnormal liver function tests (e.g., elevated AST or ALT), a standard clinical work-up to understand the etiology of the abnormality should take place per local guidelines. In many cases, elevated liver function tests may be a result of liver metastases, concomitant medications, or biliary obstruction. Dose modifications for elevated liver function tests are described in [Table 7](#).

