5.1.4 Management of Other Clinically Significant Adverse Events

See [Table 7](#) for the dose modifications for other clinically significant adverse events.

Table 7 GDC-0032 Dose Delay and Modification Guidelines for Other Clinically Significant Adverse Events

Grade	GDC-0032/ placebo
Grade 3: first event	
 • Hold GDC-0032/placebo until Grade ≤ 1. • Consider restarting at next lower dose.
Grade 3: recurrent	
 • Hold GDC-0032/placebo until Grade ≤ 1.
Grade 4: non-life-threatening	
 • Restart at next lower dose.
Grade 4: life-threatening	
 • Permanently discontinue GDC-0032/placebo.

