5.1.6 Management of Increases in QT Interval

Study drug should be discontinued in patients who develop any of the following, unless there is a clear alternative cause for the changes:

1. Sustained (at least two ECG measurements >30 minutes apart) QTcF that is >500 msec and >60 msec longer than the baseline value
2. Sustained absolute QTcF that is > 515 msec
3. An episode of torsades de pointes or a new ECG finding of clinical concern

Of note, if there is a new intraventricular conduction block, the increase in QRS complex duration should be subtracted from the QTcF change, as this represents an increase in QTcF unrelated to alterations in repolarization. Also of note, it is not uncommon to record arrhythmias such as non-sustained ventricular tachycardia, supraventricular tachycardia, pauses, or atrial fibrillation in healthy volunteers receiving placebo during periods of extended ECG monitoring. Therefore, it is critical that expert electrophysiologic advice be sought to confirm any ECG changes and to ascertain the

likelihood of a drug-induced arrhythmia versus the background occurrence of this arrhythmia. In such a situation, saving all available ECG data is highly suggested.

Management of patients with sustained QTcF prolongation should include close monitoring, with ECGs repeated at least hourly until two successive ECGs show resolution of the findings, correction of any electrolyte abnormalities, and possible discontinuation of other concomitant medications that are known to prolong the QT interval. Consultation with a cardiologist or electrophysiologist is recommended, to help in the management of such patients.

In rare circumstances, it may be acceptable to resume study drug, at a lower dose, provided that any ECG abnormalities have resolved and the patient is appropriately monitored. Clinical judgment should be applied.

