5.3.5.5 Reporting of Abnormal Liver Function Tests as Hy's Law

The finding of an elevated ALT or AST ($> 3 \times \text{ULN}$) in combination with either an elevated total bilirubin ($> 2 \times \text{ULN}$) or clinical jaundice in the absence of cholestasis or other causes of hyperbilirubinemia is considered to be an indicator of severe liver injury. Therefore, investigators must report as an adverse event the occurrence of either of the following:

- Treatment-emergent ALT or AST $> 3 \times \text{ULN}$ in combination with total bilirubin $> 2 \times \text{ULN}$
- Treatment-emergent ALT or AST $> 3 \times \text{ULN}$ in combination with clinical jaundice

The most appropriate diagnosis or (if a diagnosis cannot be established) the abnormal laboratory values should be recorded on the Adverse Event eCRF (see Section 5.3.5.1) and reported to ABCSG safety department immediately (i.e., no more than 24 hours after learning of the event), either as serious adverse event or an adverse event of special interest (see Section 5.4.2).

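### The protocol ties reporting, but no explicit dosing rule, to the Hy's law combination, and Table 7 read alone lets GDC-0032/placebo be restarted after recovery

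*Protocol*

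**What the plan says.** Section 5.3.5.5 describes ALT or AST above 3 x ULN together with total bilirubin above 2 x ULN or clinical jaundice; this finding "in the absence of cholestasis or other causes of hyperbilirubinemia is considered to be an indicator of severe liver injury". The action required there is to record it and report it within 24 hours. Section 5.2.3 lists it among the events of special interest: "Cases of potential drug-induced liver injury that include an elevated ALT or AST in combination with either an elevated bilirubin or clinical jaundice". That is again a reporting duty.

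Dosing is covered in Section 5.1.2. It asks for a work-up of cause under local guidelines. It also says "all patients must have adequate liver function as manifested by measurements of serum bilirubin", transaminases and alkaline phosphatase, at the start and while dosing continues. It then says "Dose modifications for elevated liver function tests are described in" Table 7.

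Table 7 (Section 5.1.4) is a general table by grade. After a first Grade 3 event the drug is held to Grade 1 or lower, then: "Consider restarting at next lower dose". For recurrent Grade 3 and non-life-threatening Grade 4, which appear to share one row, the drug is held to Grade 1 or lower, then: "Restart at next lower dose". Only life-threatening Grade 4 is a permanent stop.

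Section 5.1.2 also contains a sentence about patients with such findings when they enter the trial: "Separate criteria for eligibility, continued dosing, and DLT are given for patients with hepatic metastases and Grade 2 hepatic transaminase and/or alkaline phosphatase levels".

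**The concern.** The protocol names a laboratory pattern that it regards as a sign of severe liver injury, yet says nothing about study drug when the pattern appears. The one dose table it points to does not look at transaminase and bilirubin together, and its written instruction after most events is to restart at a lower dose. A site following the text could therefore re-expose a woman with operable breast cancer after such a signal without departing from any explicit rule. The decision would rest on the grade recorded and on the investigator's judgment. The sentence about separate hepatic criteria adds to the uncertainty, because it refers to continued-dosing rules that the protocol does not contain.

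**Working it through.** The protocol gives no figure to reproduce on this point. The check compares provisions, followed by a short count of possible re-exposure.

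**1. What is tied to the combination.** Sections 5.2.3 and 5.3.5.5 give reporting only. Table 7 has no row for the combination and none below Grade 3. The Grade 2 hold advice in Section 5.1.1 does not list liver events among its examples.

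**2. Provisions that could still stop dosing.**
- Adequate liver function for continued dosing (Section 5.1.2): no threshold is stated there.
- Unacceptable toxicity (Section 4.6.2): mandatory but undefined.
- Withdrawal for patient safety (Section 4.6.1): discretionary.
- Table 1: stop if specified drug-related events continue after the second reduction, so re-exposure has already happened.

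None names the combination and none forbids rechallenge.

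**3. Comparison with other dose rules.**

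| Event | Rule |
|---|---|
| Grade 4 pneumonitis, rash, stomatitis (Tables 3, 4, 6) | Permanent stop |
| Recurrent Grade 3 or Grade 4 diarrhea/colitis (Table 5) | Permanent stop |
| Grade 4 hyperglycemia (Table 2) | Resume lower only if recovered within 28 days and the Medical Monitor approves |
| QTcF criteria (Section 5.1.6) | Stop unless a clear alternative cause; resume only in rare circumstances |
| Non-life-threatening Grade 4 (Table 7) | Restart lower after recovery; no time limit or approval |
| First Grade 3 stomatitis or diarrhea (Tables 6, 5) | Restart lower after recovery |
| First Grade 3 event (Table 7) | Restart lower may be considered |
| Asymptomatic lipase/amylase elevation (Section 5.1.3) | May continue, even at the same dose, after discussion with the Medical Monitor |

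Table 7 is looser at Grade 4, and against the QTcF rule. It is not looser at a first Grade 3 event or against lipase/amylase.

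**4. The separate hepatic criteria.** Section 4.1.1 sets one limit of 1.5 x ULN for AST, ALT and alkaline phosphatase; its only hepatic exception is bilirubin in Gilbert's disease. Section 4.1.2 excludes Stage IV disease. The trial defines no DLT. The criteria said to be given are absent.

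**5. Re-exposure that Table 7 would allow.** Inputs: first reduction to 2 mg, 5 days on/2 off (Table 1); 16 weeks of dosing, to Day 112; missed doses not made up (Section 4.3.2.1); chemistry at Days 29, 57 and 85 (Appendix 1). Recovery in 14 to 28 days is an assumption. Doses = whole weeks left x 5; mg = doses x 2.
- Found Day 29, restart Day 43 to 57: 10 to 8 weeks, 50 to 40 doses, 100 to 80 mg.
- Found Day 57, restart Day 71 to 85: 6 to 4 weeks, 30 to 20 doses, 60 to 40 mg.
- Found Day 85, restart Day 99 to 113: 2 to 0 weeks, 10 to 0 doses, 20 to 0 mg.

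The full course is 16 x 5 = 80 doses x 4 mg = 320 mg.

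**6. Frequency.** No rate is given for the combination. The nearest figure is drug-related Grade 3-4 ALT or AST elevation in Section 1.7.1: about 1% of 87 (1 patient), 4% of 27 (1 patient) and none listed of 27. That is 2/141 = 1.4% (exact 95% CI 0.2% to 5.0%), on daily capsules mostly at higher doses. It measures a wider event. Purely as illustration, with 330/2 = 165 treated patients, the chance of at least one case is 1 - (1 - p)^165: 15%, 56% or 81% for assumed p of 0.1%, 0.5% or 1%.

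**The case against.** The strongest reply is that a hold is already implied. Section 4.1.1 defines adequate hepatic function at entry as bilirubin up to 1.5 x ULN (3 x ULN in Gilbert's disease) and AST, ALT and alkaline phosphatase up to 1.5 x ULN. Section 5.1.2 uses the same term for the same analytes and extends it to continued dosing. On that reading, a patient with ALT above 3 x ULN and bilirubin above 2 x ULN (outside Gilbert's disease) fails a mandatory condition. This is a fair reading, so a claim that the protocol provides no hold at all would go too far. But the link is not written down, it sits awkwardly with a table that acts only from Grade 3, and it does not address rechallenge once values recover.

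Other safeguards also count. The event is reported within 24 hours, the sponsor may assess the case independently (Section 5.5.2) and must evaluate it promptly (Section 5.7), and Table 7 is presented as guidance. Section 1.8 refers to the Investigator's Brochure for precautions, which is not at hand. These make an unsafe restart less likely; none prohibits it.

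A reader might also infer that the protocol allows rechallenge after confirmed drug-related injury. The text does not say that: Section 5.2.3 speaks of potential drug-induced injury, and Section 5.1.2 names liver metastases, other medications and biliary obstruction as possible explanations. Nor is liver injury handled more loosely than every other named toxicity, as the comparison shows. Finally, the protocol does not give CTCAE cut-offs, so which Table 7 row a given case reaches cannot be settled from it.

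**Conclusion.** The gap is real but minor. The protocol identifies a signal of possible severe liver injury, requires only that it be reported, and leaves dosing to a general table that permits or directs restart after recovery from anything it covers short of life-threatening Grade 4. Implied and general stops exist; none is explicitly linked to the combination and none bars rechallenge. The Grade 4 comparison does not depend on whether Table 7's middle entries form one row or two, since non-life-threatening Grade 4 is not a permanent stop either way; the direction to restart after recurrent Grade 3 does rest on the one-row reading.

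Possible re-exposure runs from 0 to 50 doses, depending on when the case is found and on the assumed recovery time. The frequency is unknown: the chances shown above follow from assumed rates and are not evidence that a case will occur. The reference to separate hepatic criteria is an editorial error with almost no operational effect, because the entry criteria leave essentially nobody in the group it describes.

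**What to change.** Add one row to Table 7, cross-referenced from Sections 5.1.2 and 5.3.5.5: *ALT or AST >3 x ULN with total bilirubin >2 x ULN or clinical jaundice: hold GDC-0032/placebo at once, whatever the individual grades; permanently discontinue unless another cause is established.* The model is already in Section 5.1.6: "Study drug should be discontinued in patients who develop any of the following, unless there is a clear alternative cause for the changes". Letrozole stays under Section 5.1.5.

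As a clean-up, delete the sentence in Section 5.1.2 on separate criteria for patients with hepatic metastases. Keep the adequate-liver-function requirement, and keep liver metastases among the possible causes in the work-up, since occult disease remains possible.

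The cost is one table row, two cross-references and one deleted sentence at the next amendment, with no added scheduled tests and no effect on sample size or endpoints. The small downside is that a few placebo or non-drug cases may stop GDC-0032/placebo early; the exemption for an established alternative cause limits this.
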